### **7.2.5 Sponsor Responsibility for Reporting Adverse Events**

All Adverse Events will be reported to regulatory authorities, IRB/IECs and investigators in accordance with all applicable global laws and regulations.

## **7.3 TRIAL GOVERNANCE AND OVERSIGHT**

### **7.3.1 Executive Oversight Committee**

The Executive Oversight Committee (EOC) comprises members of Sponsor Senior Management. The EOC will receive and decide upon any recommendations made by the external Data Monitoring Committee (eDMC) regarding the trial.

### **7.3.2 Data Monitoring Committee**

To supplement the routine trial monitoring outlined in this protocol, an external Data Monitoring Committee (DMC) will monitor the safety data from this trial at the appropriate frequency and for the duration required per the DMC charter. The voting members of the committee are external to the Sponsor. The members of the DMC must not be involved with the trial in any other way (e.g., they cannot be trial investigators) and must have no competing interests that could affect their roles with respect to the trial.

The DMC will make recommendations to the EOC regarding steps to ensure both subject safety and the continued ethical integrity of the trial. Also, the DMC will review interim trial results, consider the overall risk and benefit to trial participants (see Section 8.2.13 - Interim Analyses) and recommend to the EOC if the trial should continue in accordance with the protocol.

Specific details regarding composition, responsibilities and governance, including the roles and responsibilities of the various members and the Sponsor protocol team; meeting facilitation; the trial governance structure; and requirements for and proper documentation of DMC reports, minutes, and recommendations will be described in a separate charter that is reviewed and approved by the DMC. The DMC will monitor the trial at an appropriate frequency, as described in the detailed DMC charter. The DMC will also make recommendations to the Sponsor protocol team regarding steps to ensure both subject safety and the continued ethical integrity of the trial.

### **7.3.3 Clinical Adjudication Committee**

A Clinical Adjudication Committee (CAC) will evaluate the following events for the purposes of confirming them according to the criteria in Section 8.0 – Statistical Analysis Plan, as well as evaluating the presence of confounding factors.

- For severe rashes, an external clinical adjudication committee will adjudicate all cases of Stevens-Johnson Syndrome, erythroderma, toxic epidermal necrolysis, or DRESS syndrome based on photographs, biopsy results, and other available clinical data.

All personnel involved in the adjudication process will remain blinded to treatment allocation throughout the trial. Specific details regarding endpoint definitions can be found in the Adjudication Charter.

## **8.0 STATISTICAL ANALYSIS PLAN**

### **8.1 Statistical Analysis Plan Summary**

This section contains a brief summary of the statistical analyses for this trial. Full detail is in the Statistical Analysis Plan (SAP) (Section 8.2).

#### **8.1.1 Efficacy Analyses**

The primary and key secondary endpoints, primary analysis population, and statistical methods that will be employed for the efficacy analyses are presented in [Table 6](#).

There are no formal hypotheses for this trial. All efficacy measurements analyzed during the initial 104-week trial will continue to be collected and analyzed in the long term trial. The primary endpoint is the 30-Month (6 months after the primary timepoint from the initial 104-week trial) change-from-baseline treatment difference on CDR-SB.

#### **8.1.2 Safety Analyses**

The All-Subjects-as-Treated population will be employed for safety analyses. The prespecified events of interest (Tier-1 events) are 1) Microhemorrhage, superficial siderosis or macrohemorrhage; 2) vasogenic edema; 3) delirium; and 4) rash ECI. P-values and 95% confidence intervals for between-treatment differences in the percentage of subjects with events will be calculated using the Miettinen and Nurminen method [27].

#### **8.1.3 Power and Sample Size**

There are no sample size calculations for the long term trial, as there are no formal hypotheses. Subjects who complete the initial 104-week trial will be eligible for the long term trial. The number of individuals enrolled in the extension will not exceed the number enrolled in the base study.

#### **8.1.4 Interim Analyses**

The independent eDMC will routinely evaluate unblinded safety analyses of all trial subjects while the initial 104-week trial is blinded and as described in their charter. Additional safety analyses may be conducted throughout the trial as requested by the eDMC. The sponsor will be unblinded after completion of the initial 104-week trial.

## **8.2 Statistical Analysis Plan**

### **8.2.1 Responsibility for Analyses/In-House Blinding**

The statistical analysis of the data obtained from this study will be the responsibility of the Clinical Biostatistics department of the SPONSOR.

The sponsor will be unblinded after completion of the initial 104-week trial. But prior to that, the extension trial will be conducted as a double-blind study under in-house blinding procedures. Planned interim analyses are described in Section 8.2.13. Blinding to treatment assignment will be maintained at all investigational sites. The results of interim analyses will not be shared with the investigators prior to unblinding of the trial. Subject-level unblinding will be restricted to an external unblinded group of statisticians.

Treatment-level results of the interim analysis will be provided by the external statisticians to the eDMC (and any necessary consultants thereto, e.g., ophthalmologists). Limited additional SPONSOR personnel may be unblinded to the treatment level results of the interim analysis (analyses), if required, in order to act on the recommendations of the eDMC. The extent to which individuals are unblinded with respect to results of interim analyses will be documented by the external statisticians.

Prior to final study unblinding, the external statisticians will not be involved in any discussions regarding modifications to the protocol, statistical methods, identification of protocol violators, or data validation efforts.

### **8.2.2 Hypotheses/Estimation**

Objectives and hypotheses of the study are stated in Section 3.0.

### **8.2.3 Analysis Endpoints**

Efficacy and safety endpoints that will be evaluated for within- and/or between-treatment differences are listed below.

#### **8.2.3.1 Efficacy Endpoints**

It is noted that baseline refers to the baseline from the initial 104-week trial.

##### **8.2.3.1.1 Primary Efficacy Endpoint**

The primary efficacy endpoint is the change from Baseline in the CDR-SB score at Week 130.

### **8.2.3.1.2 Exploratory Efficacy Endpoints**

Exploratory endpoints include

- the time to progression to probable AD dementia as determined by investigator-diagnosis; and the following at all scheduled timepoints:
- the change from Baseline score in the CDR-SB (with the exception of Week 130 which is designated as the primary endpoint);
- the change from Baseline score in the CCS-3D;
- the change from Baseline score for the composite cognition subscale (memory, orientation, judgment and problem solving) and composite functional subscale (home and hobbies, personal care and community affairs) of the CDR;
- the change from Baseline score for: ADCS-ADLMCI, ADAS-Cog13, Number Cancellation, MMSE, CCS-2D, and NPI;
- Modified RUD Lite, HEA, and EQ-5D;
- the change from Baseline score for the three domain z-scores of the CCS-3D (episodic memory, executive function, and attention/processing speed);
- the change from Baseline score for the domain-specific individual components of the CCS-3D: Immediate Word Recall (ADAS-Cog), Delayed Word Recall (ADAS-Cog), Word Recognition (ADAS-Cog), and Orientation (ADAS-Cog), Digit Span Test (Forwards), DSC, Digit Span Test (Backwards), Trails A Test, Trails B Test, COWAT, and CERAD Verbal Fluency Test.

### **8.2.3.2 Safety Endpoints**

Refer to Section 8.2.8 for initial description of safety measures. It is noted that baseline refers to the baseline from the initial 104-week trial.

### **8.2.3.3 Derivations of Efficacy Endpoints**

For the handling of missing data within an endpoint (i.e., if an individual subquestion needed for a total score is missing) see Section 8.2.7.5

The CCS-3D will be calculated as the mean of three domain z-scores (episodic memory, executive function, and attention processing). In a similar fashion, each of these three domain z-scores will be calculated as the mean of domain specific tests (after transformation to z-scores), as follows:

Episodic Memory: Immediate Word Recall, Delayed Word Recall, Word Recognition, and Orientation (all from ADAS-Cog);

Executive Function: Digit Span Test (Backwards), Trails B Test, COWAT, CERAD Verbal Fluency Test;

Attention/Processing Speed: Trails A Test, Digit Span Test (Forwards), DSC

The z-scores [(observed value - baseline mean)/ baseline standard deviation)] for each of the individual component tests will be calculated at each timepoint using the baseline mean and standard deviation of all treated subjects. Prior to taking the average of three domain scores for the computation of CCS-3D, each of the three domain scores will be normalized in a similar fashion.

The CCS-2D endpoint will be constructed by averaging the z-scores from five component tests: Immediate Word Recall (ADAS-Cog), Word Recognition (ADAS-Cog), Orientation (ADAS-Cog), COWAT, and CERAD Verbal Fluency.

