## **4.2.2 Rationale for Endpoints**

### **4.2.2.1 Outcome Measures Rationale**

As in the protocol for the initial 104-week trial, the primary outcome measure is the change from Baseline in the Clinical Dementia Rating Scale Sum of Boxes (CDR-SB) score at 130 weeks. The CDR-SB is highly relevant clinically and has been shown to worsen over time in this patient population.

Progression to probable AD dementia will be included in the long term trial as an exploratory objective. This study will use both NINCDS ARDRA and Diagnostic and Statistical Manual of Mental Disorders, 4th Edition, Text Revision (DSM-IV-TR) criteria to define probable AD dementia. Unlike the initial 104-week trial, cases of progression in the long term trial

will not be reviewed by an adjudication committee; therefore, the final decision on progression will be the opinion of the investigator or qualified designee. The progression endpoint will provide useful information for patients and physicians for understanding the effects of MK-8931.

Other clinical measures include the following: a) the composite cognition score (based on the mean of the three domain z-scores from tests of episodic memory, working memory/executive function, and attention/psychomotor speed) and b) the Alzheimer's Disease Cooperative Study Activities of Daily Living Inventory (ADCS ADLMCI) (mild cognitive impairment [MCI] version) score. Previously conducted trials have demonstrated that cognition and function are relevant dimensions of clinical progression in this patient population. Regarding cognition, prior studies of MCI have used some version of the Alzheimer's Disease Assessment Scale Cognitive subscale (ADAS-Cog). Because of the well-known issue with sensitivity of the ADAS-Cog, many studies have also included additional, standard cognitive tests. Several methods have been proposed to combine the ADAS-Cog with the additional tests to generate a composite cognition score. While intensive ongoing research may clarify the optimal approach, this protocol will calculate the average z-score of three cognitive domains thought to be involved in prodromal AD based on modeling suggesting this is superior to the ADAS-Cog alone.

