#### **7.1.2.3.5 Trail Making Test (A&B)**

The Trail Making Test [18; 19], a brief paper/pencil assessment of visual scanning (Part A) and visuomotor sequencing (Part B), will be administered to the subject and scored by a qualified, trained rater according to the instructions in the Manual of Assessments. Additional detailed information concerning administration, scoring and documentation may also be provided by the rater training vendor.

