## **8.2.4 Analysis Populations**

### **8.2.4.1 Efficacy Analysis Populations**

The Full Analysis Set (FAS) population will serve as the primary population for the analysis of efficacy data in this study. The FAS population for a given endpoint consists of all randomized subjects who:

- receive at least one dose of study treatment,
- have both 1) a baseline measurement for the analysis endpoint and 2) at least one within-analysis-window ( $\pm 6$  weeks) post-dose, post-randomization observation for the analysis endpoint, and
- are PET positive.

All available observations from the initial 104-week trial will be included in the relevant model-based FAS analyses. Observations from the long term trial will be included according to the principles outlined above, with the following additional requirement: the subject must have taken at least one dose of study medication within the 28 days preceding the 104-week visit and within the 28 days following the 104-week visit.

The Modified Full Analysis Set (MFAS) population will be utilized for sensitivity analyses and is defined identically to the FAS population with one exception: patients will only be required to have either 1) a baseline measurement for the analysis endpoint or 2) at least one within-analysis-window ( $\pm 6$  weeks) post-dose, post-randomization observation for the analysis endpoint, but not necessarily both.

The MFAS population will be utilized to conduct sensitivity analyses in this study for the primary endpoint (CDR-SB 30-Month CFB).

Though no Per-Protocol analyses are planned, a list of protocol violations/violators will be maintained. The final determination on protocol violations will be made prior to the final unblinding of the database and will be documented in a separate memo.

Subjects will be included in the treatment group to which they are randomized for the analysis of efficacy data using the FAS population.

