For Baseline ADCS-ADLMCI only (from the initial 104-week trial): Past experience indicates that some subquestions on the ADCS-ADLMCI may mistakenly be omitted at the time of administration. Should this occur at baseline, there will be no opportunity to employ the stated LOCF approach. To avoid a missing total score on the ADCS-ADLMCI (and the subsequent removal of the subject from the primary ADCS-ADLMCI population), the worst possible score for that subquestion will be imputed. Note that this imputation approach will only be implemented for ADCS-ADLMCI (given the relatively small impact of the individual subquestions on the overall score) and only at baseline. A total score will only be computed if the number of missing subtotals is strictly less than three.

Endpoint specific details are as follows:

ADAS-Cog and MMSE: The site will be instructed to enter the worst possible score if the subject is unwilling or unable to answer a subquestion due to reasons related to the area the subquestion is trying to address. If the subject is unable to answer a subquestion for some

other reason, then the site will be instructed to leave the subquestion as missing. For both the ADAS-Cog and the MMSE, a total score will be calculated if the original number (prior to applying LOCF) of missing subtotals is strictly less than three.

CCS-3D: If no more than one test is missing within a domain(s), LOCF will be applied to that individual test. Values will not be carried forward for more than one visit. If more than one test is missing within a domain (prior to applying LOCF), then the overall z-score for that domain will be computed as missing. The overall CCS-3D will be computed as missing if any domain score is missing. Note that, in general and unless otherwise noted, the application of LOCF to these individual tests is solely for the computation of the domain z-scores and ultimately the CCS-3D. LOCF will not be applied to these individual tests for the analyses of the individual tests themselves (e.g., LOCF may be applied to the Delayed Word Recall test for the computation of the Episodic Memory domain z-score and ultimately the CCS-3D, but would not be applied for the purposes of analyzing the Delayed Word Recall component individually).

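### Does averaging cognition z-scores without a stated test direction (SAP Section 8.2.3.3) call for a change to the plan?

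*Combined protocol and SAP*

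**What the plan says.** Section 8.2.3.3 gives one standardisation for every component, "The z-scores [(observed value - baseline mean)/ baseline standard deviation)] for each of the individual component tests will be calculated at each timepoint", with the mean and standard deviation taken from all treated subjects at baseline. Domain scores are plain means of these z-scores. Each domain is then normalised again, and CCS-3D is the mean of the three.

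- Episodic memory uses four ADAS-Cog items.
- The executive domain is given as "Executive Function: Digit Span Test (Backwards), Trails B Test, COWAT, CERAD Verbal Fluency Test".
- Attention/processing speed uses Trails A, Digit Span Forwards and Digit Symbol-Coding.
- CCS-2D averages five z-scores: "Immediate Word Recall (ADAS-Cog), Word Recognition (ADAS-Cog), Orientation (ADAS-Cog), COWAT, and CERAD Verbal Fluency".

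Neither this section nor Sections 4.2.2.1, 7.1.2.3.3 to 7.1.2.3.8, 8.2.3.1.2, 8.2.7.2 or 8.2.7.6 gives the direction of a component, a reversal step, or the polarity of the composite. Scoring is referred elsewhere. The Trail Making Test, for example, "will be administered to the subject and scored by a qualified, trained rater according to the instructions in the Manual of Assessments". For the ADAS-Cog and MMSE, Section 8.2.7.6 says "The site will be instructed to enter the worst possible score if the subject is unwilling or unable to answer a subquestion" in certain circumstances, without saying which end of the scale is worst.

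**The concern.** Read as a literal programming instruction, the section is complete except for the sign. If two tests in one average run in opposite directions, a patient who worsens on both contributes a rise on one and a fall on the other, and the average loses part of the change or points the wrong way.

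That is more than a labelling matter. A pure reversal of a composite leaves a two-sided p-value alone, but cancellation alters the estimate and the p-value. CCS-3D, CCS-2D and the domain scores are analysed with the primary model (Section 8.2.7.2), and CCS-3D also goes into the Week 130 subgroup analyses (Section 8.2.12). A reader of the plan alone cannot tell which sign favours treatment.

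**Working it through.** The plan states no figure for these scores, so there is nothing to reproduce. The check applies the derivation algebraically.

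**Inputs from Section 8.2.3.3:** the z-score formula, the component lists, plain means, and re-normalisation of domains before CCS-3D.

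**Assumptions, not in the documents:**

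- Directions: ADAS-Cog items and Trails A and B higher-is-worse; Digit Span, Digit Symbol-Coding, COWAT and CERAD fluency higher-is-better. Other combinations are shown below.
- A common correlation ρ between tests once they are aligned.
- Every test worsens by 1 baseline SD.

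**Raw means with the formula taken literally, both instruments opposed:**

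- Memory: (1 + 1 + 1 + 1)/4 = +1.00
- Executive: (-1 + 1 - 1 - 1)/4 = -0.50
- Attention: (1 - 1 - 1)/3 = -0.33
- CCS-2D: (1 + 1 + 1 - 1 - 1)/5 = +0.20

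With aligned signs, each of these is -1.00.

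**Re-normalisation for CCS-3D.** A domain mean with sign vector a over k tests has baseline SD √(a′Ra)/k, where R is the correlation matrix. At ρ = 0.3:

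- Aligned: memory and executive SD = √(7.6)/4 = 0.689, giving -1/0.689 = -1.451 each. Attention SD = √(4.8)/3 = 0.730, giving -1.369. CCS-3D = (-1.451 - 1.451 - 1.369)/3 = -1.42.
- Literal: memory +1.451. Executive SD = √4/4 = 0.5, giving -0.5/0.5 = -1.000. Attention SD = √(2.4)/3 = 0.516, giving -0.333/0.516 = -0.645. CCS-3D = (1.451 - 1.000 - 0.645)/3 = -0.065.

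**How far this depends on the assumed directions** (uniform 1-SD decline; CCS-3D at ρ = 0.3):

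| Tests opposed to the rest | Memory | Executive | Attention | CCS-3D | CCS-2D |
|---|---|---|---|---|---|
| None (already aligned) | -1.00 | -1.00 | -1.00 | -1.42 | -1.00 |
| ADAS-Cog items only | +1.00 | -1.00 | -1.00 | -0.46 | +0.20 |
| Trails only | -1.00 | -0.50 | -0.33 | -1.03 | -1.00 |
| Both | +1.00 | -0.50 | -0.33 | -0.065 | +0.20 |

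If only the ADAS-Cog items are opposed, no domain is mixed internally. If only Trails is opposed, CCS-2D is untouched. Damage to CCS-3D, CCS-2D and two domain scores together needs both.

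**How far it depends on the other assumptions.** With both opposed, literal CCS-3D runs from +0.14 at ρ = 0 to -0.22 at ρ = 0.7, against -1.91 to -1.13 aligned, so even its sign turns on ρ. The pattern of decline matters as well. Take CCS-2D at ρ = 0.5, in units of its own baseline SD. The literal SD is √3/5 = 0.346 and the aligned SD is √15/5 = 0.775.

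- Uniform decline: (0.20/0.346)/(1.00/0.775) = 45% of the aligned size, reversed.
- Decline in the three ADAS-Cog items only: the raw means are +0.6 and -0.6, so the ratio is 0.775/0.346 = 2.24, or 224% of the aligned size, reversed, with no loss of signal.

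The possible effect therefore runs from none, through near-complete cancellation, to a reversed score of more than twice the standardised size. These figures describe decline, not a difference between arms, and baseline SD only stands in for the SD of change.

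**What the plan implies about intent.** Section 4.2.2.1 adopts the three-domain average "based on modeling suggesting this is superior to the ADAS-Cog alone". A score whose domains cancel would defeat that purpose. Section 8.1.1 says "All efficacy measurements analyzed during the initial 104-week trial will continue to be collected and analyzed in the long term trial", and Section 8.2.4.1 says "All available observations from the initial 104-week trial will be included in the relevant model-based FAS analyses". Baseline throughout is the initial trial's baseline. The composite must therefore be one variable with one definition across both parts, and the natural reading is that its derivation, signs included, comes from the initial trial.

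**The case for a change.** The best case for an amendment is that the omission is real and cheap to repair. Section 8.1 says full detail is in Section 8.2, and 8.2.3.3 is otherwise a complete recipe. The Manual of Assessments is cited for administering and scoring tests, not for building composites, and 8.2.3.3 points neither to it nor to the initial trial. Nor is the plan careful about sign everywhere. In Section 8.2.7.5 the tipping-point constant is subtracted from active-arm values to disadvantage the active arm, although Table 8 has CDR-SB rising by 2.13 with progression.

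The gap in the text stands. The tipping-point wording is a separate matter: it gives a reason to check sign handling in the programs, but it is not evidence that the composites are mis-signed. The step from silence to a wrong result does not stand. It needs test directions that the documents do not give, no alignment in the Manual or in the initial trial's derivation, and an analyst who averages opposed tests without noticing. The last is unlikely, and the data offer a check, because Section 8.2.3.1.2 has every CCS-3D component analysed separately. A composite moving against its own components would show.

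**Conclusion.** No change to the plan follows. Section 8.2.3.3 leaves the direction of the component tests and composites unwritten, but this is a detail that analysts fill sensibly by aligning signs before averaging, most naturally by keeping the initial trial's convention.

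The size of any effect cannot be fixed from the documents. It is zero if scores are already aligned; otherwise it depends on assumed scoring directions, correlations and patterns of decline. The reach is limited to exploratory results: CCS-3D, CCS-2D, the executive and attention domain scores, and the CCS-3D subgroup summaries. CDR-SB, ADAS-Cog13, MMSE and the single-test analyses do not use these averages, and Sections 8.1.1 and 8.2.10 state that the extension has no formal hypotheses.

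The conclusion assumes that the Manual of Assessments or the initial trial's derivation, neither of which is available here, sets the polarity or that the programmers apply the usual alignment. Evidence that the composites had been programmed without alignment would change it.
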